### 14 BIOMARKER ANCILLARY STUDY

As an ancillary study to the POINT Trial, participants will be asked to donate a one-time blood sample collected at time of enrollment in trial; no follow up is conducted. The objective is to determine whether clopidogrel-resistant genotypes modify the stroke prevention response in high-risk TIA and minor ischemic stroke patients.

- (1) **PRIMARY OUTCOME**: Relative risk of vascular outcome events for carriers of specific ABCB1 and CYP2C19 genotypes vs. non-carriers among subjects receiving clopidogrel.
- (2) **SECONDARY OUTCOME**: Subgroup analysis by enrolling/index event type, performed separately for TIA and minor ischemic stroke cohorts.

Approximately one-quarter to one-third of subjects are expected to be carriers of the CYP2C19 poor metabolizer allele, which has been associated with an increased risk of vascular events with hazard ratios (HR) ranging from 1.5 to 3.6 across studies. Of primary interest is the relative risk of vascular outcome events for carriers versus non-carriers amongst those receiving clopidogrel. Assuming approximately 80% of the remaining POINT patients consent to participate in this proposal, then the total sample contributing to the repository is approximately 2,534 (anticipating that this substudy will start enrolling August 2012). Cox proportional hazard regression will be used to model the time to composite event of ischemic stroke, MI, or ischemic vascular death. The model will be fit using all available data from both treatment groups and will adjust for treatment group (clopidogrel or placebo), allele type (carrier vs non-carrier), and the interaction of carrier and treatment group. From this model, the relative risk (hazard ratio) for carriers receiving clopidogrel relative to the noncarriers receiving clopidogrel (reference group) will be estimated. This model will also adjust for other covariates as specified in section 12.1.5. The following suspected significant confounders are: age, time from symptom onset to randomization, African Americans, those previously taking aspirin, those with index TIA vs. minor ischemic stroke. A model building approach will be used, considering first the univariate association of each potential confounder. The allele type should have no affect on outcome rates for the placebo group, but the model will be fit with all available data to improve the variance estimates and thus improve statistical power.

Of secondary interest is a subgroup analysis by the enrolling/index event type (either TIA or minor ischemic stroke cohort). The same analysis will be performed separately for the TIA cohort and the minor ischemic stroke cohort.

Given a sample size of approximately 2,534 total, there will be 1,267 patients (1/2) randomized to clopidogrel. Given the expected event rate of 12% in the clopidogrel group, a total of 149 ischemic outcome events are anticipated in the clopidogrel group. Assuming 30% of subjects are carriers of the CYP2C19 poor metabolizer allele, a 0.05 alpha level two-sided log-rank test for equality of survival curves will have at least 80% power to detect a difference between the relative risk for carriers receiving

clopidogrel relative to the noncarriers receiving clopidogrel (reference group) when the true hazard ratio is 1.64. **Table 3** below gives the minimum detectable hazard ratio under various assumptions about the total number of samples available and the proportion of carriers.

| Table 3. Minimum Detectable Hazard Ratios with 80% Power |                                 |                              |  |                      |  |  |  |  |  |  |
|--|---------------------------------|------------------------------|--|----------------------|--|--|--|--|--|--|
| Total number of samples in biomarker study               | Expected N in clopidogrel group | Proportion
of
Carriers | Expected
number
of vascular
outcome | Hazard Ratio
(HR) |  |  |  |  |  |  |
|  |                                 |                              | events                                       |                      |  |  |  |  |  |  |
| 2534   | 1267                            | 0.2                          | 152  | 1.76                 |  |  |  |  |  |  |
| 2534   | 1267                            | 0.3                          | 152  | 1.64                 |  |  |  |  |  |  |
| 2534   | 1267                            | 0.4                          | 152  | 1.59                 |  |  |  |  |  |  |
| 2534   | 1267                            | 0.5                          | 152  | 1.58                 |  |  |  |  |  |  |

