14.1 Optional POINT Biomarkers Ancillary Study

Participants who consent to the POINT trial will be asked to consent to an optional ancillary study consisting of a one-time venous blood sample of approximately 10 mL, collected at the time of enrollment in the trial. Subjects indicating consent to the Biomarkers Study by checking the appropriate box will be asked for a one-time sample of approximately 10 mL of peripheral venous blood. Consent will be collected for both the blood sample and the optional ancillary study. Those patients who decline the ancillary study will not be prohibited from participating in the POINT Trial.

Plasma and DNA will be prepared for genotyping analysis and stored at the Neurogenetics Laboratory at the Mayo Clinic in Jacksonville, Florida (MCF) as required by Federal and state regulations. The study samples will be used for testing the specific hypothesis as to whether clopidogrel resistant genotypes modify the stroke prevention response in high-risk TIA patients. Subjects will be assigned numbers which will be placed on the sample labels and allow researchers to link the sample to the encrypted ancillary study database. No personal identifying information will be kept with the samples. Results of the genotyping analysis will not be shared with subjects.

Of primary interest is the relative risk of vascular outcome events for carriers (of specific ABCB1 and CYP2C19 genotypes) versus non-carriers amongst those receiving clopidogrel. Of secondary interest is a subgroup analysis by the enrolling/index event type (either TIA or minor ischemic stroke cohort) performed separately for the TIA cohort and the minor ischemic stroke cohort.

Genotyping results (raw data and summary data) will be provided to the POINT Trial Principal Investigator and lead statistician for incorporation into the existing trial data set into WebDCU. Analyses exploring an interaction between genotypes and treatment response will be done jointly, including testing of inherited clopidogrel resistance. This would be the first systematic study of clopidogrel resistance in the setting of stroke prevention following TIA. The stored samples will also be a resource for future studies in this patient population.

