### 5.3 Re-estimation of the Sample Size Result

As stipulated in **section 5.2,** following the first interim analysis, the maximum sample size has been re-estimated to be 5,840 subjects.

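### The biomarker substudy asks whether genotype modifies clopidogrel's effect, but its primary and only powered contrast is carriers versus non-carriers within the clopidogrel arm

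*SAP*

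**What the plan says.** SAP section 14 sets the aim: "The objective is to determine whether clopidogrel-resistant genotypes modify the stroke prevention response in high-risk TIA and minor ischemic stroke patients". It then names the primary outcome as a contrast inside one arm: "Of primary interest is the relative risk of vascular outcome events for carriers versus non-carriers amongst those receiving clopidogrel".

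The analysis is a Cox model fitted to both treatment groups. Besides treatment, it contains "allele type (carrier vs non-carrier), and the interaction of carrier and treatment group". From that model the SAP extracts one quantity: "the relative risk (hazard ratio) for carriers receiving clopidogrel relative to the noncarriers receiving clopidogrel (reference group) will be estimated". On the placebo arm it says: "The allele type should have no affect on outcome rates for the placebo group". Its stated reason for keeping placebo patients in the model is better variance estimates and hence power.

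Power is given only for the within-clopidogrel contrast. With 2,534 samples, 1,267 of them on clopidogrel, a 12% event rate and 30% carriers, the SAP claims at least 80% power at a hazard ratio of 1.64. The text says "a total of 149 ischemic outcome events are anticipated in the clopidogrel group", whereas Table 3 uses 152. Section 5.3 records that "the maximum sample size has been re-estimated to be 5,840 subjects".

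Protocol section 14.1 has the same primary contrast and adds: "Analyses exploring an interaction between genotypes and treatment response will be done jointly".

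**The concern.** Modification is a comparison of treatment effects between carriers and non-carriers, which is the carrier-by-treatment interaction. The within-clopidogrel hazard ratio is the product of two things: any effect that carrier status has on risk regardless of treatment, and any change in clopidogrel's effect. It equals the second alone only if the first is absent.

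Genotype is not randomized, and the SAP itself lists suspected confounders for this model. Placebo patients are asked for samples too, so the assumption can be checked. With the interaction in the model, placebo patients add little precision to the within-clopidogrel contrast; their main value is as that check.

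Protocol section 2.4.2 shows that the two questions can have different answers. It reports that carriers of a reduced-function variant appear to have excess risk while on clopidogrel. It then cites a study concluding that such variants do not modify the drug's efficacy or safety. Section 14.1 presents the substudy as the first systematic study of clopidogrel resistance in this setting, so a significant primary contrast would readily be read as resistance even if it were prognosis.

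**Working it through.** **Inputs from the documents**
- SAP section 14 and Table 3: 1,267 patients on clopidogrel, 12% event rate, 152 events (149 in the text), carrier share a = 0.30, two-sided alpha 0.05, 80% power, hazard ratio 1.64.
- SAP section 5.1, Table 1: placebo event proportion 15.24%. With 1,267 placebo patients this gives 0.1524 x 1,267 = 193 events.

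**1. Reproduce the plan's figure.** Schoenfeld's formula with unequal allocation gives a detectable HR of exp[(1.960 + 0.842) / sqrt(D a (1-a))]. With D = 152, D a (1-a) = 152 x 0.3 x 0.7 = 31.92, and exp(2.802 / 5.650) = 1.64. For 20, 30, 40 and 50% carriers the formula gives 1.765, 1.642, 1.590 and 1.575, against 1.76, 1.64, 1.59 and 1.58 in Table 3. Table 3 reproduces.

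**2. Primary contrast when the allele is only prognostic.** Assume the same carrier hazard ratio h in both arms, so that the ratio of hazard ratios is 1 and nothing is modified. The chance that the unadjusted within-arm test is significant is Phi(ln h x sqrt(31.92) - 1.960).
- h = 1.2: Phi(0.182 x 5.650 - 1.960) = Phi(-0.93) = about 18%
- h = 1.3: Phi(0.262 x 5.650 - 1.960) = Phi(-0.48) = about 32%

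The values of h are assumptions; the documents give none.

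**3. Interaction on the SAP's own inputs.**
- Var(log ratio of HRs) = 1/31.92 + 1/(193 x 0.21) = 0.0313 + 0.0247 = 0.0560, so SE = 0.237.
- Power at a ratio of 1.64: Phi(0.495 / 0.237 - 1.960) = Phi(0.13) = about 55% (about 59% if the variance is taken under the alternative).
- Detectable ratio at 80% power: exp(2.802 x 0.237) = about 1.94, ranging from 2.14 at 20% carriers to 1.84 at 50%.

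**4. Do the old inputs matter?** Some of what follows is inferred.
- Samples: 2,534 / 0.8 = 3,167.5 patients remaining. This fits the 4,150 design with about 982 already enrolled. At 5,840: 0.8 x (5,840 - 982.5) = 3,886 samples, or 1,943 on clopidogrel.
- Event rate, low: 530 / 5,840 = 9.08% overall. With the 23% relative reduction, placebo is 2 x 9.08 / 1.77 = 10.3% and clopidogrel is 7.9%.
- Event rate, high: SAP Table A.1 needs 6,311 patients at a 10% placebo rate. Then 10% x 6,311 / 5,840 = 10.8% for placebo and x 0.77 = 8.3% for clopidogrel.

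| Quantity (30% carriers) | SAP inputs | Updated, inferred |
|---|---|---|
| Clopidogrel events | 152 | 153 to 162 |
| Within-arm detectable HR | 1.64 | 1.64 to 1.62 |
| Within-arm power at 1.64 | 80% | 80% to 82% |
| Interaction power at 1.64 | 55% | 56% to 58% |
| Interaction detectable ratio | 1.94 | 1.93 to 1.90 |

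**5. 149 versus 152.** 12% x 1,267 = 152. The design treatment rate in SAP Table A.1, 11.73%, gives 11.73% x 1,267 = 149. With 149 events, power at 1.64 is 79.0%.

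**The case against.** The strongest reply is that little is missing. The model includes both arms and the interaction, the placebo-arm carrier hazard ratio comes from the same fit, and Protocol section 14.1 already foresees interaction analyses. All of this stands. A reader might infer that the substudy cannot separate prognosis from modification. The documents do not support that: the primary contrast cannot, but the planned model can.

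Next, the placebo assumption has a basis. Protocol section 9.3.1 describes clopidogrel as a prodrug activated by CYP2C19, and section 7.4.1 prohibits open-label clopidogrel after randomization. The assumption is therefore reasoned. It is still an assumption, it can be tested on data the substudy will hold, and the mechanism given does not cover the ABCB1 genotypes that the primary outcome also names.

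Third, section 14 lists African Americans among the suspected confounders, so ancestry is not ignored. Adjustment is by a model-building step and covers one group, so it limits confounding without removing it.

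Finally, the 18% and 32% are illustrations, not predictions. The prognostic hazard ratios are hypothetical and the test is unadjusted, whereas the planned model is adjusted. Nor does the SAP contain a rule that turns a significant within-arm result into a declared finding of modification. It would be wrong to read these figures as the plan's false-positive rate.

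**Conclusion.** The concern holds as a mismatch between objective and estimand. The objective is modification, while the primary and only powered quantity is a within-arm hazard ratio that equals modification only if carrier status has no effect under placebo. The interaction that answers the objective is in the model but has no named test, no primary status and no stated power. On the SAP's inputs that power is about 55% at a ratio of 1.64, so a reader who sees only 1.64 at 80% power cannot tell how weakly the stated question is addressed.

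A reader might also infer from the outdated inputs that the power result fails. It does not. The larger sample and the lower event rate nearly cancel, leaving the within-arm detectable hazard ratio at about 1.62 to 1.64. That rests on a back-calculated 982 patients enrolled before the substudy, 80% consent and inferred event rates. Pairing the old 2,534 samples with the lower rate would suggest a large loss of power, but it mixes two designs. The 149 and 152 events fit two roundings of the same rate, and the difference costs about one point of power.

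This is worth correcting because it changes what the substudy may conclude. It is ancillary and does not touch the trial's primary efficacy or safety results.

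**What to change.** In SAP section 14, and to match in Protocol section 14.1:
- Base any claim that genotype modifies the response on the carrier-by-treatment interaction from the planned Cox model, reported as a ratio of hazard ratios with a 95% CI.
- Report the carrier versus non-carrier hazard ratio in the clopidogrel and placebo arms side by side, as supportive. This also shows whether the placebo assumption is tenable.
- State the interaction's power: about 55% at a ratio of 1.64, and 80% only at about 1.94, on the SAP's inputs.

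If the within-clopidogrel contrast is kept as primary, the objective should be reworded as prognosis by genotype among patients given clopidogrel.

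Housekeeping only: reconcile 149 with 152 events; replace the 2,534 samples and 12% rate with values for the 5,840 design, using actual substudy enrolment; and correct the covariate cross-reference, since section 12.1.5 now covers geographic region and covariates are in 12.1.6.

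The cost is wording; no new data and no change of model are needed. The real downside is that the stated power for the objective falls, and the substudy may be unable to settle modification at effect sizes that the within-arm contrast could detect.

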### 16 APPENDIX: SAMPLE SCENARIOS FOR INTERIM STOPPING VERSUS SAMPLE SIZE INCREASE

Table A.1 Sample Scenarios for Interim Stopping versus Sample Size Increase at the First Interim Analysis

|          | Observed
Placebo Rate
(Hypothetical
Values) | Upper 99% CL
(for observed
placebo rate) | Observed
Trt Rate
(Hypothet
ical
Values) | interim | Interim
Analysis
(Stop if | (1/3) under
the
original | Re-
estimated
N at final
analysis
(530
events) for
90% Power
(HR=0.75) |  | Conditional Power (2/3) under the original | DSMB
Recommendations
at 2 nd Interim
Analysis |
|----------|--|--|--|---------|---------------------------------|--------------------------------|---|--|--|---|
| SCENARIO | values)  | piacebo rate)                                  | values)  | atrisk  | 3./1)                           | design                         | (HK=U.75)   | at 1 Interim Analysis  | design                                     | Continue as   |
| 1        | 15.24%   | 18.4%  | 11.73%   | 1383    | 1.89                            | 0.94                           | N/A   | Continue as planned  | 0.99                                       | planned   |
| 2        | 14.0%  | 17.1%  | 14.0%  | 1332    | 0.00                            | 0.59                           | N/A   | Continue as planned  | 0.06                                       | Stop for futility   |
| 3        | 14.0%  | 17.0%  | 12.0%  | 1435    | 1.10                            | 0.84                           | N/A   | Continue as planned  |  | Continue as
planned  |
| 4        | 12.0%  | 14.6%  | 10.0%  | 1696    | 1.32                            | 0.88                           | N/A   | Continue as planned  | 0.86                                       | Continue as planned   |
| 5        | 10.0%  | 12.4%  | 12.5%  | 1658    | -1.63                           | 0.18                           | 6,311   | Stop for futility  | N/A  | N/A   |
|          |  |  |  |         |                                 |                                |   | Consider safety profile,
Perform another interim analysis
sooner than planned, |  | Continue as planned (with increased sample                        |
| 6        | 10.0%  | 12.2%  |  |         |                                 | l l                            | -   | discuss increasing N   | 0.77                                       | size)   |

The assumed placebo rate of the original design was 15.24% with a 95% CI (13.63%, 16.85%).

POINT Trial Statistical Analysis Plan (Version 8: Sept 2017)

Scenario 1 assumes the observed placebo and treatment groups are as hypothesized under the original design.

### Scenario 2

177 primary events are observed and the first interim analysis is performed. The observed placebo rate is 14%. Although 14% is less than the expected placebo event rate of 15.24%, the 99% upper confidence limit overlaps with those of the assumed rate (13.63%, 16.85%). A sample size increase is not warranted. The log rank test is performed and the corresponding Z value is 0. Since 0 is less than 3.71 (the critical value for the O'brien-Flemming stopping boundary at look 1), the trial is not stopped for overwhelming efficacy. The conditional power under the original design is 0.59 at the time of the 1st interim analysis which does not meet the criteria to stop for futility (>0.20). The DSMB recommends the trial be continued. After 353 events are observed, second interim analysis is performed. At this time the conditional power is 0.06 (which is < 0.20). The trial is stopped for futility.

### Scenario 4

177 adjudicated primary events are observed and the first interim analysis is performed. The log rank test is performed and the corresponding Z value is 1.32. Since 1.32 is less than 3.71 (the critical value for the O'brien-Flemming stopping boundary at look 1), the trial is not stopped for overwhelming efficacy. The conditional power is computed to be 0.88 under the design alternative which is greater than the criteria to stop for futility (>0.20). The observed placebo rate is 12%. Although 12% is less than the expected placebo event rate of 15.24%, the 99% upper confidence limit (14.6%) overlaps with those of the assumed rate (13.63%, 16.85%). The trial is continued and the next interim look is planned after 2/3 of events have been observed.

#### Scenario 6

177 primary events are observed and the first interim analysis is performed. The log rank test is performed and the corresponding Z value is 1.15. Since 1.15 is less than 3.71 (the critical value for the O'brien-Flemming stopping boundary at look 1), the trial is not stopped for overwhelming efficacy. The conditional power is computed to be 0.85 which is greater than the criteria to stop for futility (0.85>0.20). Thus, no formal stopping criteria have been met.

However, the observed placebo rate is 10%. The 99% upper confidence limit around the current placebo estimate (12.2%) does not overlap with those of the assumed rate (13.63%, 16.85%). This suggests a sample size increase is needed. The sample sizes under various placebo event rates are given in Figure 2. To achieve at least 90% power, more than 6,300 patients would be needed to observe 530 events given the current estimate of the placebo event rate (10%). However, given the substantial increase in sample size required to attain 90% power, the DSMB decides to look again sooner than planned after 50% of events (or 265 events) have been observed.

Table A.2 Conditional Power given RRR of 23% and 10% for various placebo proportions

|      | Hazard | Placebo | Trt    | Expected N at first interim analysis | Z Log-
Rank |         | t
(177 | Conditional Power | Conditional
Power
under
the original | Conditional
Power
under |
|------|--------|---------|--------|--------------------------------------|----------------|---------|-----------|-------------------|---|-------------------------------|
| RRR  | Ratio  | Rate    | rate   | Number at risk                       | Test           | p-value | events)   | under the null    | design  | current trend                 |
| 0.23 | 0.75   | 15.24%  | 11.73% | 1383                                 | 1.89           | 0.0586  | 0.33      | 0.13              | 0.94  | 0.94                          |
| 0.23 | 0.75   | 14%     | 10.78% | 1506                                 | 1.88           | 0.0602  | 0.33      | 0.13              | 0.94  | 0.94                          |
| 0.23 | 0.75   | 12%     | 9.24%  | 1756                                 | 1.86           | 0.0628  | 0.33      | 0.13              | 0.94  | 0.93                          |
| 0.23 | 0.75   | 10%     | 7.70%  | 2108                                 | 1.84           | 0.0654  | 0.33      | 0.13              | 0.94  | 0.93                          |
| 0.10 | 0.9    | 15.24%  | 13.72% | 1288                                 | 0.79           | 0.4281  | 0.33      | 0.03              | 0.79  | 0.22                          |
| 0.10 | 0.9    | 14%     | 12.60% | 1403                                 | 0.79           | 0.4313  | 0.33      | 0.03              | 0.78  | 0.22                          |
| 0.10 | 0.9    | 12%     | 10.80% | 1636                                 | 0.78           | 0.4362  | 0.33      | 0.03              | 0.78  | 0.21                          |
| 0.10 | 0.9    | 10%     | 9.00%  | 1964                                 | 0.77           | 0.4410  | 0.33      | 0.03              | 0.79  | 0.21                          |

The table A.2 shows the conditional power when the difference in treatment groups is equivalent to a RRR of 23% (HR=0.75) for various placebo rates. The Conditional power is constant given a constant RRR (rows 1-4). Decreasing the RRR to 10% results in a decrease in conditional power, but again the conditional power is constant for a fixed RRR (rows 5-8).

